3. OBJECTIVES, ENDPOINTS, AND ESTIMANDS

Objectives	Endpoints	Estimands
Primary:	Primary:	Primary:

 To compare the efficacy of PF-07321332/ritonavir to placebo for the treatment of symptomatic COVID-19 in nonhospitalized adult participants with COVID-19 who are at low risk of progression to severe disease. 	
 Time (days) to sustained alleviation of all targeted COVID-19 signs/symptoms through Day 28. 	
 The difference in median time (days) to sustained alleviation of all targeted COVID-19 signs and symptoms through Day 28 between PF-07321332/ritonavir and placebo in nonhospitalized adult patients with COVID-19 who are at low risk of progression to severe disease at baseline and were treated ≤ 5 days after COVID-19 symptom onset. This will be estimated irrespective of adherence to randomized treatment.
Secondary:	Secondary:	Secondary:

 To describe the safety and tolerability of PF-07321332/ritonavir relative to placebo in the treatment of nonhospitalized symptomatic adult participants with COVID-19 who are at low risk of progression to severe disease. 	
 Incidence of TEAEs. Incidence of SAEs and AEs leading to discontinuations. 	
 Not Applicable.

 To compare PF-07321332/ritonavir versus placebo for COVID-19-related hospitalization and all-cause mortality in nonhospitalized adult participants with COVID-19 who are at low risk of progression to severe disease. 	
 Proportion of participants with COVID-19-related hospitalization or death from any cause through Day 28. Proportion of participants with death (all cause) through Week 24. 	
 The difference in proportions of patients experiencing COVID-19-related hospitalization or death from any cause through Day 28 in nonhospitalized adult patients with COVID-19 who are at low risk of progression to severe disease and were treated ≤ 5 days after COVID-19 symptom onset. This will be estimated without regard to adherence to randomized treatment. Not Applicable

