4. STUDY DESIGN

4.1. Overall Design

This Phase 2/3, randomized, double-blind, placebo-controlled study in approximately 1980 symptomatic low risk participants with COVID-19 who are nonhospitalized will determine the efficacy, safety, and tolerability of PF-07321332/ritonavir compared with placebo. Eligible participants with a confirmed diagnosis of SARS-CoV-2 infection will be

randomized (1:1) to receive PF-07321332/ritonavir or placebo orally q12h for 5 days (10 doses total). Randomization will be stratified by geographic region, by vaccination status and by COVID-19 symptom onset (≤ 3 days vs > 3 to 5 days). Throughout the study period, provision will be made to allow study visits to be conducted at a participant's home or at another nonclinic location approved by the investigator where possible when participants are unwilling or unable to attend a clinic visit.

The total study duration is up to 24 weeks and includes a screening period of no more than 48 hours, administration of study intervention through Day 5 or Day 6, efficacy assessments through Day 28, a safety follow-up period through Day 34, and long-term follow up at Weeks 12 and 24.

An independent E-DMC will review unblinded data for this Study C4671002 to ensure the safety of participants throughout the duration of the study. In addition to up to weekly reviews of safety, the E-DMC will review the following:

- Sentinel cohort safety review: The E-DMC will review unblinded safety data after approximately the first 100 randomized participants have completed through Day 10. Whether enrollment is paused for this review will depend on the successful completion of the Study C4671005 sentinel cohort (after approximately the first 60 randomized participants have completed through Day 10). If the Study C4671005 sentinel cohort safety review has successfully completed and no clinically significant safety signals have been identified prior to enrollment of the first 100 participants in this Study C4671002, the study will continue without pause. Otherwise, enrollment of Study C4671002 will be paused pending the E-DMC review of safety data. After review of the sentinel cohort in this Study C4671002, the frequency of safety reviews may be reduced subsequently based on E-DMC recommendations.

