9.2. Analysis Sets

For purposes of analysis, the following analysis sets are defined:

Participant Analysis Set	Description
Full Analysis Set (FAS)	All participants randomly assigned to study intervention regardless of whether or not study intervention was administered.
Safety Analysis Set (SAS)	All participants randomly assigned to study intervention and who take at least 1 dose of study intervention. Participants will be analyzed according to the study intervention they received. A randomized but not treated participant will be excluded from the safety analyses.
Modified Intent -To-Treat (mITT)	All participants randomly assigned to study intervention who take at least 1 dose of study intervention and with at least 1 postbaseline visit through Day 28 who were treated ≤ 3 days after COVID-19 symptom onset. Participants will be analyzed according to the study intervention to which they were randomized.
Modified Intent -To-Treat 1 (mITT1)	All participants randomly assigned to study intervention, who take at least 1 dose of study intervention. Participants will be analyzed according to the study intervention to which they were randomized.
Per-Protocol (PP)	All participants in the mITT1 set without major protocol violations considered to impact the interpretation of the primary efficacy endpoint. Protocol deviations will be reviewed to generate the list of participants with significant deviations to be excluded from the PP analysis set. The PP exclusion criteria will be finalized prior to breaking the blind.

Both the mITT1 and PP analysis sets will be used in the analyses of the primary efficacy endpoint, with the mITT1 being primary. For proportion of COVID-19-related hospitalization or death from any cause endpoint, mITT1 will be used. For all other efficacy analysis, the mITT1 analysis set will be used, as defined in the SAP. The Safety Analysis Set will be used in the analyses of the safety data.

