4. ANALYSIS SETS (POPULATIONS FOR ANALYSIS)

Data for all participants will be assessed to determine if participants meet the criteria for inclusion in each analysis population prior to unblinding and releasing the database and classifications will be documented per standard operating procedures.

Population	Description
Full Analysis Set (FAS)	All participants randomly assigned to study intervention regardless of whether or not study intervention was administered.
Safety Analysis Set (SAS)	All participants who receive at least 1 dose of study intervention. Participants will be analyzed according to the intervention they actually received. A randomized but not treated participant will be excluded from the safety analyses.

Population	Description
Modified Intent -To Treat (mITT)	All participants randomly assigned to study intervention who take at least 1 dose of study intervention and with at least 1 postbaseline visit through Day 28 who were treated ≤ 3 days after COVID symptoms onset. Participants will be analyzed according to the study intervention to which they were randomized.
Modified Intent-To-Treat (mITT1)	All participants randomly assigned to study intervention, who take at least 1 dose of study intervention. Participants will be analyzed according to the study intervention they were randomized.
Per-Protocol (PP)	All participants in the mITT1 set without important protocol deviations considered to impact the interpretation of the primary efficacy endpoint. Protocol deviations will be reviewed to generate the list of participants with significant deviations to be excluded from the PP analysis set. The PP exclusion criteria will be finalized prior to breaking the blind.

Both the mITT1 and PP analysis sets will be used in the analyses of the primary efficacy endpoint, with the mITT1 being primary. For proportion of COVID-19 related hospitalization or death from any cause and all other efficacy endpoints, mITT1 will be used. The Safety Analysis Set will be used in the analyses of the safety data.

Multiple Enrollers:

If a participant enters/is randomized into Study C4671002 more than once or is enrolled in Study C4671002 and in 1 or 2 other Phase 2/3 nirmatrelvir/ritonavir studies:

- (1) The primary and key secondary efficacy analyses will be performed by considering all enrolled participants (subject IDs) as independent participants.

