- If the participant's last observed data is prior to Day 21, then impute as an event with event day as day of last observed data +1.
- If the participant's last observed data is on or after Day 21, then no imputation for event will be done and participant remains censored at day of last observed data.

6.2.4. Proportion of Participants with Death (all cause) through Week 24

Descriptive statistics will be used to summarize proportion of death through Week 24 by treatment group using mITT1 populations. Treatment comparisons between groups will be presented as odds ratios with 95% confidence intervals and P-value based on logistic regression model (if data permit).

If zero counts are observed in either treatment group, the Fishers Exact test will be performed (instead of logistic regression) and p-value provided.

The participants enrolled under or after protocol amendment 6 will not include this summary.

6.2.5. Number of COVID-19 Related Medical Visits through Day 28

The number of COVID-19 related medical visits will be analyzed with a negative binomial regression model, using the log total number of days of data collection as the participant offset variable (if data permit). The resulting analysis will evaluate the difference in estimated rate of number of medical visits between treatment groups and the associated 95% CI. The analyses will be done using mITT1 populations.

6.2.6. Number of Days of Hospital and ICU Stay in Participants with COVID-19 Related Hospitalization

Health resource utilization data will be summarized by treatment group for each treatment. The analyses will be done using mITT1 populations. Descriptive statistics (ie, mean, median, range) will be used to summarize this endpoint.

The resulting analysis will provide the estimated difference in the average of number of days stayed in the hospital between treatment groups, with p-value and 95% confidence interval. The analyses will be done using the mITT1 population.

6.2.7. Proportion of Participants with Severe Signs/symptoms Attributed to COVID19 through Day 28

Participants will record a daily severity rating of their symptom severity over the past 24 hours based on a 4-point scale in which 0 is reported if no symptoms were present; 1 if mild; 2 if moderate; and 3 if severe. A participant with severe score for any targeted symptoms post-baseline will be counted as severe.

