Proportion of participants with COVID-19 related hospitalization or death from any cause through Day 28	Sensitivity analysis for key secondary endpoint	mITT1	If the participant's last observed data is prior to Day 21, then impute as an event with event day as day of last observed data +1. If the participant's last observed data is on or after Day 21, do not impute an event and	Kaplan-Meier method

Endpoint	Analysis Type	Population	Data Inclusion and Rules for Handling Intercurrent Events and Missing Data	Analysis Model
			participant remains censored at day of last observed data.	
Proportion of participants with COVID-19 related hospitalization or death from any cause through Day 28	Sensitivity analysis for key secondary efficacy analysis for multiple enrollers	mITT1 including only data with first randomization within the study	All data collected will be included regardless of intercurrent events. Kaplan-Meier method to take account of losses to follow-up.	Kaplan-Meier method
Proportion of participants with COVID-19 related hospitalization or death from any cause through Day 28 by vaccination status	Subgroup analysis for key secondary endpoint	mITT1	Subset analysis identified in Section 6.4.	Kaplan-Meier method
Proportion of participants with COVID-19 related hospitalization or death from any cause through Day 28	Supplemental analysis for key secondary efficacy endpoint	PP	Participants who discontinued the study before Day 28 without event will be censored at Day 25.	Kaplan-Meier & Log rank test
Proportion of participants with death (all cause) through Week 24.	Secondary analysis	mITT1	All data collected will be included regardless of intercurrent events exclude participants enrolled under PA6	Logistic Regression
Number of COVID-19 related medical visits through Day 28.	Secondary analysis	mITT1	All data collected will be included regardless of intercurrent events. Missing data will not be imputed.	Descriptive statistics (based on negative Binomial Model)
Number of days in hospital and ICU stay in participants with COVID-19 related hospitalization through Day 28.	Secondary analysis	mITT1	All data collected will be included regardless of intercurrent events. Missing data will not be imputed.	Descriptive statistics
Proportion of participants with severe signs/symptoms attributed to COVID-19 through Day 28.	Secondary Efficacy Analysis	mITT1	All data collected will be included regardless of intercurrent events, LOCF for missing data.	Logistic regression model

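### The SAP leaves Amendment 6 enrollees out of the Week 24 all-cause death summary without a reason, although the protocol endpoint, the follow-up schedule and the mITT1 set all include them

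*SAP*

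**What the plan says.** **Protocol.** The text supplied is Amendment 6: Appendix 11 lists Amendments 1 to 5 as past. Section 3 has the secondary endpoint "Proportion of participants with death (all cause) through Week 24", with no limit by amendment; the synopsis and section 9.3.3 list it the same way. On the analysis set, section 9.2 says: "For all other efficacy analysis, the mITT1 analysis set will be used, as defined in the SAP". Section 4.1 plans "long-term follow up at Weeks 12 and 24". The Schedule of Activities and section 8.3.1 put a vital-status check at each of those times. None of these passages treats Amendment 6 enrollees differently.

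**SAP.** Section 6.2.4 will "summarize proportion of death through Week 24 by treatment group using mITT1 populations". Section 4 defines mITT1 as everyone randomised who took at least one dose. Section 6.2.4 then ends with "The participants enrolled under or after protocol amendment 6 will not include this summary". The Appendix 1 row for this endpoint gives mITT1 as the population and, as its data rule, "All data collected will be included regardless of intercurrent events exclude participants enrolled under PA6".

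**Timing.** Protocol 4.1 and SAP 2.2 both place the final analysis after all participants have completed or withdrawn. Protocol 4.4 counts a participant as complete only after the last scheduled visit.

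**The concern.** A secondary mortality endpoint is defined for the whole trial, the data for it are scheduled for the whole trial, and the named analysis set is everyone randomised and dosed. The SAP then removes a block of those participants by the protocol version under which they enrolled, without explanation. The resulting table would cover a narrower group than the protocol endpoint describes, and the group left out would be the most recent enrollees.

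Where a late death would be seen also matters. Deaths through Day 28 count for everyone in the hospitalisation-or-death endpoint (SAP 6.2.3). The Week 24 summary is the only efficacy analysis that reaches later deaths, so for an excluded participant no efficacy table would show one. The adverse event summaries do not fill the gap: SAP 6.6.1 limits them to events starting by Day 34, and Protocol 8.3.1 requires reporting during long-term follow-up only for SAEs judged related to treatment.

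**Working it through.** The plan states no sample size, event count or power for Week 24 death, so there is no figure to reproduce for this endpoint. The check is mainly a comparison of texts, followed by an illustration of size.

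**1. What the exclusion means.** Read literally, the closing sentence of SAP 6.2.4 is garbled. The Appendix 1 row settles it: "exclude participants enrolled under PA6". Both are operative text, so this is not a stray line or a change-log entry. They differ in scope. Section 6.2.4 covers enrolment under or after Amendment 6, Appendix 1 only enrolment under it.

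**2. Texts side by side.**

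| Item | Source | Restricted by amendment? |
|---|---|---|
| Week 24 death endpoint | Protocol 1.1, 3, 9.3.3 | No |
| Weeks 12 and 24 vital status | Protocol 1.3, 4.1, 8.3.1 | No |
| Set for other efficacy analyses | Protocol 9.2 (mITT1) | No |
| mITT1 definition | SAP 4 | No |
| Week 24 death summary | SAP 6.2.4, Appendix 1 | Yes |

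**3. Could timing explain it?** An exclusion would make sense if later enrollees could not have reached Week 24 by the analysis. The final analysis waits for everyone to complete or withdraw, so on the documents this reason is not available. The Amendment 6 entry in the SAP version history restates follow-up to Week 24 and the death endpoint, and gives no reason either.

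**4. Does the plan foresee anyone in the excluded group?** The Appendix 1 footnote defines a combined mITT1 population from before and after Amendment 6 (dated 09 Jun 2022), so such participants are at least anticipated.

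**5. Size.** Planned total: 1880 / (1 − 0.05) = 1979, which agrees with the stated figure of about 1980. The number enrolled under Amendment 6 is not given. Taking the 1140 as enrolled before the Amendment 5 extension, the most that could be excluded is 1980 − 1140 = 840. The minimum is 0. The intermediate values below are assumptions, and the denominators ignore participants who were never dosed. The last column is the exact two-sided 95% upper limit on the death proportion when an arm has no deaths, 1 − 0.025^(1/n).

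| Excluded (assumed) | Share of 1980 | Left in total | n per arm | Upper limit, zero deaths |
|---|---|---|---|---|
| 0 | 0% | 1980 | 990 | 0.37% |
| 400 | 20.2% | 1580 | 790 | 0.47% |
| 840 | 42.4% | 1140 | 570 | 0.65% |

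The zero-death case is relevant: Protocol 2.2.2 reports no deaths through Day 28 among 333 + 329 = 662 participants at the first interim analysis. The mix also shifts. The pre-extension share of the denominator is 1140/1980 = 57.6% with no exclusion, 1140/1580 = 72.2% with 400 excluded, and 100% with 840 excluded.

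**The case against.** **The protocol leaves this analysis to the SAP.** Section 9.3.3 defers the details of this endpoint to the SAP, section 9 allows the SAP to modify the outlined analyses where appropriate, and the estimand entry for this endpoint is not applicable. This stands. A reader might infer that the SAP breaches the protocol, but it does not; this is an unexplained departure. The clause does not, however, resolve the SAP's conflict with its own mITT1 set.

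**The exclusion is disclosed.** In both SAP places it sits beside the mITT1 label. This stands: the documents do not support reading the label as misleading. The restricted set simply has no name of its own.

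**Late deaths are not hidden.** Death is a listed reason for leaving the study (Protocol 7.2). SAP 6.5.2 presents withdrawal reasons and summarises disposition in the full analysis set, SAP 5.2 lists disposition events by participant, and the E-DMC reviews all deaths (Protocol 10.1.5.1). This stands. What is lost is the death's place in the efficacy mortality summary.

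**There is no bias between arms.** Protocol version at enrolment is fixed before treatment and applies equally to both arms, so the comparison remains randomised within those kept. The endpoint is reported with nominal p-values and is outside the Hochberg list in SAP 5.1. This stands.

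**The number may be trivial.** Amendment 6 is dated 139 days after Amendment 5. At the original planning rate of 30 per day, the remaining 840 would take 840 / 30 = 28 days, so few or none may have enrolled under Amendment 6. Actual accrual is not given and the Appendix 1 footnote anticipates some, so this limits the size of the point without removing it.

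**Conclusion.** The point holds as an unexplained restriction that should be removed or justified. The SAP drops randomised, dosed participants from a secondary mortality summary although the protocol endpoint, the visit schedule and the named analysis set all include them, and the stated timing of the final analysis gives no reason for it. The consequence is a reduced denominator, lower precision, and the absence from the efficacy mortality summary of any death after Day 28 in an excluded participant.

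The size is unknown. It runs from nothing to at most about 840 of 1980 on planned numbers, an upper bound that assumes everyone beyond the 1140 enrolled under Amendment 6. A reader might go further and infer a distorted treatment comparison or concealed deaths. The documents support neither: the rule is the same for both arms, and disposition outputs would still show the deaths. The reference to all participants being followed to Week 24 means the planned schedule, with withdrawals and losses as the usual exceptions.

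**What to change.** 1. Delete the closing sentence of SAP 6.2.4 and the exclusion phrase in the Appendix 1 row for Week 24 death, so that the summary covers all mITT1 participants.
2. Add to SAP 6.2.4 that the number with unknown vital status at Week 24 will be reported by arm. This matters because the general last-observation-carried-forward rule in SAP 5.3, if applied here, would count a participant last known alive as alive at Week 24. A Kaplan-Meier estimate would be an optional addition.
3. If there is a reason for the exclusion that the documents do not record, state it in SAP 6.2.4, give the restricted set its own name, make 6.2.4 and Appendix 1 agree on its scope, and reconcile both with the protocol's endpoint list and its Week 12 and Week 24 schedule.

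The first route costs two deletions and one added sentence, and uses data already scheduled for collection. The second is also a text change, but may require the protocol to be aligned.

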9.1.1.2. Secondary Estimands

The estimands associated with the secondary objectives are as follows:

- The difference in proportions of patients experiencing COVID-19 related hospitalization or death from any cause through Day 28 in nonhospitalized adult patients with COVID-19 who are at low risk of progression to severe disease and were treated ≤ 5 days after COVID-19 symptom onset. This will be estimated without regard to adherence to randomized treatment.
- The difference in the estimated rate of the number of COVID-19-related medical visits through Day 28 in nonhospitalized adult patients with COVID-19 who are at low risk of progression to severe disease and were treated ≤ 5 days after COVID-19 symptom onset. This will be estimated without regard to adherence to randomized treatment.
- The difference in the estimated rate of number of days in hospital and ICU stay in patients with COVID-19 related hospitalization through Day 28 in nonhospitalized adult patients with COVID-19 who are at low risk of progression to severe disease and were treated ≤ 5 days after COVID-19 symptom onset. This will be estimated without regard to adherence to randomized treatment.

Estimands for the other outcome measures are not presented.

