The estimand for the number of COVID-19-related medical visits through Day 28 is the difference in estimated rate of number of COVID-19 related medical visits through Day 28 in nonhospitalized adult patients with COVID-19 who are at low risk of progression to severe

disease and were treated ≤ 5 days after COVID-19 symptom onset. This will be estimated without regard to adherence to randomized treatment.

The statistical methodology for this endpoint will be as follows:

The number of COVID-19 related medical visits will be analyzed with a negative-binomial regression model, using the log-total number of days of data collection as the participant offset variable. The resulting analysis will provide the estimated difference in rate of medical visits between treatment groups and the associated 95% CI.

Number of days in hospital and ICU stay in participants with COVID-19-related hospitalization through Day 28

Summary statistics for this endpoint will be provided in support of the number of COVID-19-related medical visits through Day 28.

Details on the definitions and analyses of the following secondary endpoints will be described in the SAP.

- Time (days) to sustained resolution of all targeted COVID-19 signs/symptoms through Day 28.
- Proportion of participants with severe signs/symptoms attributed to COVID-19 through Day 28.
- Duration of each targeted COVID-19 sign/symptom.
- Progression to a worsening status in 1 or more self-reported COVID-19 associated symptoms through Day 28.
- Proportion of participants with a resting peripheral oxygen saturation $\geq 95\%$ at Days 1 and 5.
- Proportion of participants with death (all cause) through Week 24.
- PF-07321332 PK in plasma and whole blood (if feasible).
- Viral titers measured via RT-PCR in nasal swabs over time.

CCI

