2.1.2. Secondary Estimands

The estimands associated with the secondary objectives are as follows:

- *The difference in proportions of patients experiencing COVID-19-related hospitalization or death from any cause through Day 28 in nonhospitalized adult patients with COVID-19 who are at low risk of progression to severe disease and were treated ≤ 5 days after COVID-19 symptom onset. This will be estimated without regard to adherence to randomized treatment.*
- *The difference in estimated rate of number of COVID-19-related medical visits through Day 28 in nonhospitalized adult patients with COVID-19 who are at low risk of progression to severe disease at baseline. This will be estimated irrespective of adherence to randomized treatment.*
- *The difference in the estimated rate of number of days in hospital and ICU stay in patients with COVID-19-related hospitalization through Day 28 in nonhospitalized adult patients with COVID-19 who are at low risk of progression to severe disease and were treated ≤ 5 days after COVID-19 symptom onset. This will be estimated without regard to adherence to randomized treatment.*

Estimands for the other outcome measures are not presented.

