3.2. Secondary Endpoint(s)

- *Incidence of treatment emergent adverse events (TEAEs).*
- *Incidence of SAEs and AEs leading to discontinuations.*

- *Proportion of participants with COVID-19 related hospitalization or death from any cause through Day 28.*
- *Proportion of participants with death (all cause) through Week 24.*
- *Number of COVID-19 related medical visits through Day 28.*
- *Number of days in hospital and ICU stay in participants with COVID-19 related hospitalization through Day 28.*
- *Proportion of participants with severe signs/symptoms attributed to COVID-19 through Day 28.*
- *Time (days) to sustained resolution of all targeted COVID-19 signs/symptoms through Day 28.*
- *Duration of each targeted COVID-19 sign/symptom.*
- *Progression to a worsening status in 1 or more self-reported COVID-19-associated symptoms through Day 28.*
- *Proportion of participants with a resting peripheral oxygen saturation $\geq 95\%$ at Days 1 and 5.*
- *PF-07321332 PK in plasma and whole blood (if feasible).*
- *Viral titers measured via RT-PCR in NP/nasal swabs over time.*

CCI [REDACTED]

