5.2.4. Analyses for Count Endpoints

For count endpoints (ie, number of COVID-19 related medical visits through Day 28 and number of days of hospitalizations/ICU stay in participant with COVID-19-related hospitalization through Day 28), a negative binomial regression model analysis, using the

log total number of days of data collection as the participant offset variable, will be conducted and the difference in estimated rate will be provided.

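### The hospital-days endpoint is worded for admitted participants only, yet SAP 6.2.6 promises a between-arm p-value and CI, and the denominator and method are not settled

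*SAP*

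**What the plan says.** The endpoint in SAP 3.2 is "Number of days in hospital and ICU stay in participants with COVID-19 related hospitalization through Day 28". The estimand (Protocol 9.1.1.2, repeated in SAP 2.1.2) has the same restriction on a rate scale: "The difference in the estimated rate of number of days in hospital and ICU stay in patients with COVID-19 related hospitalization". The heading of SAP 6.2.6 carries the restriction as well.

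SAP 6.2.6 first asks for descriptive statistics and then adds "The resulting analysis will provide the estimated difference in the average of number of days stayed in the hospital between treatment groups", with a p-value and 95% confidence interval. That sentence covers hospital days and does not mention ICU days. The next one reads "The analyses will be done using the mITT1 population", and mITT1 (SAP 4) is everyone randomised and dosed.

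Other sections differ on method. SAP 5.2.4 lists "number of days of hospitalizations/ICU stay in participant with COVID-19-related hospitalization through Day 28" among the count endpoints for negative binomial regression, with log days of data collection as offset. Protocol 9.3.3 says "Summary statistics for this endpoint will be provided in support of the number of COVID-19-related medical visits through Day 28". Protocol 9.1 and SAP 5.1 say the endpoint will be summarized, and SAP Appendix 1 gives descriptive statistics with no imputation of missing data.

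**The concern.** Admission happens after randomisation, and the plan expects treatment to change it: the re-sizing in Protocol 9.5 and SAP 2.3 assumes a reduction of 70% or more in hospitalization or death. The participants admitted in each arm are therefore selected by an outcome of treatment. A between-arm test within that subset loses the protection of randomisation. It takes no account of admissions prevented, and it can turn against the drug if those prevented are mainly short ones.

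A second problem applies on any reading. The programmer is not told whether participants never admitted count as 0 days or are left out, or which of the stated methods applies. A difference in average stay also does not estimate the rate difference named in the estimand.

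**Working it through.** **1. The sections side by side**

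| Section | Restricted to the hospitalised? | Method |
|---|---|---|
| Protocol 9.1.1.2, SAP 2.1.2 (estimand) | Yes | Difference in rate, hospital and ICU days |
| Protocol 9.1, Protocol 9.3.3, SAP 5.1 | Yes | Summary only |
| SAP 5.2.4 | Yes | Negative binomial, days-of-data offset |
| SAP 6.2.6 | Heading yes; mITT1 named twice | Descriptive, plus difference in average hospital days with p-value and CI, no test named |
| SAP Appendix 1 | Endpoint label yes; mITT1 column | Descriptive |

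No row contains a rule of 0 days for participants not admitted.

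**2. Size of the admitted subset.** The plan gives this endpoint no sample size, power or length-of-stay assumption. The overall figures reproduce: 1140 + 740 = 1880, and 1880/0.95 = 1979 against the stated 1980. With 1:1 allocation, 1880/2 = 940 per arm. For 26 events and a 70% reduction, x + 0.3x = 26 gives x = 20 on placebo and 6 on active, treating every event as an admission. At the 45% interim (Protocol 2.2.2) the admitted were 2 of 333 (0.60%) v 8 of 329 (2.43%), a 75% lower risk.

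**3. Precision among the admitted.** The 95% half-width is t × SD × √(1/a + 1/b). For 6 v 20, t on 24 df is 2.064 and the root is 0.465. Assumed SDs of 3, 5 and 8 days give 2.9, 4.8 and 7.7 days. For 2 v 8 they give 5.5, 9.1 and 14.6 days.

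**4. Fixed examples (stays assumed)**
- All stays 8 days. Among the admitted: 8.0 v 8.0, difference 0. Per 100 participants: 20×8/940 = 17.0 on placebo and 6×8/940 = 5.1 on active.
- Placebo has fourteen 5-day and six 15-day stays; the drug prevents only the short ones. Among the admitted: (70+90)/20 = 8.0 on placebo and 90/6 = 15.0 on active, 7.0 days against the drug. Per 100 participants: 160/940 = 17.0 and 90/940 = 9.6, ratio 0.56 in favour of the drug.

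**5. Simulation.** 4000 runs, 940 per arm, expected admissions 20 v 6, Welch tests. Assumed placebo stays are gamma-distributed: 70% short (mean 5 days) and 30% long (mean 15), held between 1 and 28 days. The admitted-only columns use runs with at least two admissions in each arm.

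| Admissions prevented | Mean difference among admitted | Estimate against drug | Nominally significant harm | All participants with zeros: favours drug |
|---|---|---|---|---|
| Regardless of length | 0.0 days | 47% | 1% | 99% |
| Short ones preferentially (60% of remaining stays long) | +3.0 | 83% | 10% | 96% |
| Short ones only | +6.9 | 99% | 56% | 89% |

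The all-participant comparison of means is nominally significant for the drug in 64%, 43% and 25% of runs respectively.

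**The case against.** A reader might infer that the plan definitely tests only hospitalised participants. It does not say so. SAP 6.2.6 names mITT1 twice, and a rate with a days-of-data offset fits an analysis of everyone. That part of the objection stands: restriction to the admitted is a reading, though the more natural one. Naming mITT1 does not by itself cancel an endpoint's own restriction. SAP 6.2.9 also uses mITT1, for symptom durations defined only in participants with that symptom at baseline. If everyone was meant, the zero rule is missing, and so is a named test in 6.2.6 for data about 98.6% zero (1 − 26/1880).

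A reader might also infer that ICU days are tested in SAP 6.2.6, or that fewer admissions would go unseen. Neither is supported. The inference sentence covers hospital days only. Admissions or death is the key secondary endpoint, estimated in all mITT1, and medical visits (which include hospitalization under Protocol 8.1.2) are compared in the same set.

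Nor does an all-participant test add much power. In a separate simulation with equal stays averaging about 8 days, a rank test with zeros rejected in 82.7% of runs, but so did a Wald test of the admission proportions alone; Welch with zeros rejected in 67.5%. In the second fixed example the all-participant mean difference has p = 0.20. The reason to change is validity and clarity.

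Finally, most sections already treat the endpoint as descriptive, and it supports the medical-visits endpoint with nominal p-values. This limits the severity. It does not remove the inferential sentence in SAP 6.2.6 or the model in SAP 5.2.4.

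**Conclusion.** The point holds as a defect of definition and consistency. As worded, the endpoint and estimand condition on a post-randomisation outcome, SAP 6.2.6 attaches a p-value and CI to a comparison of hospital days, and the sections disagree on method. If the natural reading is followed, about 6 people are compared with 20, without randomisation. The result can show no difference or apparent harm while total hospital days fall.

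The 6 v 20 split assumes 26 events, a 70% reduction and every event an admission. The direction and size of any distortion rest on assumed lengths of stay: when admissions are prevented regardless of length, the expected difference is zero rather than harmful. The loss of the randomised comparison does not depend on those assumptions. Severity is minor to moderate, since the endpoint is supportive, carries no alpha and lies outside the Hochberg list in SAP 5.1.

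**What to change.** Remove the p-value and CI for length of stay among the admitted from SAP 6.2.6, drop the endpoint from the negative binomial model in SAP 5.2.4, and keep it descriptive as in Protocol 9.1 and 9.3.3, SAP 5.1 and SAP Appendix 1. Reword the rate-difference estimand in Protocol 9.1.1.2 and SAP 2.1.2 to match.

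If a between-arm comparison is wanted, define days in hospital, and separately in ICU, through Day 28 per mITT1 participant, with 0 for those not admitted. State how deaths are handled, since death can shorten days in hospital, and name one method. A permutation test with a bootstrap CI for mean days per participant would serve. Use the same wording in Protocol 9.1.1.2 and SAP 2.1.2, 3.2, 5.2.4, 6.2.6 and Appendix 1, with stay among the admitted shown beside it without a p-value.

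The cost is wording only: Protocol 8.1.2 already collects admission and discharge dates and ICU status.
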